³CMP includes glucose, blood urea nitrogen, creatinine, sodium, potassium, chloride, bicarbonate, calcium, total protein, albumin, serum bilirubin, alkaline phosphatase, ALT, AST

⁴A single 12 lead ECG should be performed at screening and day 1 of every cycle +/- 2 weeks.

⁵Echocardiogram should be performed at screening and every three cycles +/- 2 weeks

⁶Response to therapy will be assessed by interval imaging studies every 2 cycles (8 weeks)+/- 2 weeks with response evaluated using RECIST version 1.1. Radiologic imaging will include a CT chest +/- abdomen/pelvis depending on sites of disease with or without contrast. If an appropriate imaging study is performed early for any reason (i.e. hospitalization), it can be used for disease assessment. CT scans should be completed if the patient comes off study for any reason other than progression. If a CT scan was completed within the last 8 weeks, it will not need to be repeated.

⁷ B-HCG testing (serum or urine) should be performed only in women of child bearing potential.

⁸ Tumor biopsy will be performed within 3 months of study initiation (unless archived tissue is available from a biopsy obtained after progression on erlotinib) and at time of progression +/- 4 weeks. Both patients on the phase 1 and phase 2 portion of the study will have biopsies performed.

⁹ IMPACT bloods will be drawn at screening for next-generation sequencing based testing.

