Progressive Disease (PD):	Appearance of one or more new lesions and/or unequivocal progression of existing non-target lesion

Table 12.3 Best Overall Response

Target Lesions	Non-Target Lesions	New Lesions	Overall Response
CR	CR	No	CR
CR	Incomplete/SD	No	PR
PR	Non-PD	No	PR
SD	Non-PD	No	SD
PD	Any	Yes or No	PD
Any	PD	Yes or No	PD
Any	Any	Yes	PD

Evaluation of Best Overall Response: The best overall response is the best response recorded from the start of treatment until disease progression, as defined in **Table 12.3**.

Evaluation of Toxicity: All patients who receive at least one dose of treatment with erlotinib and trametinib will be evaluable for toxicity.

Progression Free Survival (PFS): Duration of time from first treatment to time of progression or death, whichever occurs first.

Overall Survival (OS): Duration of time from first treatment to time of death.

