13.0 CRITERIA FOR REMOVAL FROM STUDY

Patients may withdraw from the study at any time. Other reasons for study discontinuation include but are not limited to:

- Change in patient eligibility
- Non-compliance with the defined treatment plan
- Protocol violation
- Investigator's decision based on patient's best interest
- Withdrawal of consent
- Severe, unexpected toxicities/side effects
- Lost to follow up
- Death
- Progression of disease (defined by RECIST 1.1)

For the Phase 1 portion of the study, patients who withdraw from the study for reasons other than DLT without completing a full treatment cycle will be replaced.

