Methods: A Simon optimal two-stage trial design will be utilized to assess the primary endpoint of response rate (RECIST 1.1 CR+PR). This study will test the null hypothesis of 5% response rate against the alternative hypothesis of 25% response rate for patients with acquired resistance. A null hypothesis of 5% was chosen because all eligible patients have demonstrated progression and lack of response to erlotinib. The most effective treatment for both EGFR T790M positive and negative patients is afatinib and cetuximab which has a response rate of 29% but results in significant adverse events¹⁸. Subsequently, an alternative hypothesis of 25% was chosen for this study. The design chosen has a 10% type I error (falsely accepting a non-promising therapy), 10% type II error (falsely rejecting a promising therapy), for 90% power. In the first stage of this design, 9 patients will be treated. If 0 responses are seen in the first 9 patients, the trial will be stopped and declared negative. If at least 1 response is observed, than an additional 15 patients will be accrued to the second stage. At the end of the study, if 3 or more patients have a response out of a total of 24 patients enrolled, the combination of trametinib and erlotinib will be considered worthy of further investigation. Overall survival and time to progression will be estimated using the Kaplan-Meier method, with the follow-up starting at the initiation of therapy. Patients will be censored at the time of the last on-study evaluation if they do not experience the event of interest. Safety and tolerability will be summarized using descriptive statistics. The toxicities and the adverse events will be assessed for each patient according to the NCI CTCAE version 4.0 criteria. All correlative aims are exploratory and will be hypothesis-generating only.

Given an expected accrual rate of 2 patients per month, the accrual to the phase 2 portion of the study will be completed in about 6-12 months.

Correlatives: For the correlative studies, the analysis is primarily exploratory and hypothesis generating. Correlative studies will be performed on all patients participating in both the phase 1 and 2 portions of this clinical trial.

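### Section 14 estimates time to progression rather than PFS as defined, and censors patients removed without RECIST progression as if removal were uninformative; whether deaths, including those after removal, count is not settled

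*Combined protocol and SAP*

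**What the plan says.** **Definition.** Section 12 defines PFS as "Duration of time from first treatment to time of progression or death, whichever occurs first". It sets no limit to events seen on study. PFS is also a secondary objective in Section 14.

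**Analysis.** The methods paragraph of Section 14 names a different quantity: "Overall survival and time to progression will be estimated using the Kaplan-Meier method, with the follow-up starting at the initiation of therapy". The next sentence gives one censoring rule for both outcomes: "Patients will be censored at the time of the last on-study evaluation if they do not experience the event of interest". The reason for leaving plays no part in it.

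**Removal.** The removal reasons in Section 13 include "Severe, unexpected toxicities/side effects", "Investigator's decision based on patient's best interest" and non-compliance. None of these requires RECIST progression, which is a separate item on the list.

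**Off-study scan.** Table 10.1, footnote 6, states "CT scans should be completed if the patient comes off study for any reason other than progression", and then: "If a CT scan was completed within the last 8 weeks, it will not need to be repeated". Routine scans are every 8 weeks, plus or minus 2 weeks.

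**Later follow-up.** Section 10.0 sets a final visit within 30 days of the last dose. After that it describes follow-up only for treatment-related adverse events that are still ongoing and for later treatment-related serious ones. Neither Section 10.0 nor Section 14 states tumour imaging or survival contact after that visit.

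**The concern.** Two things do not fit together.

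First, time to progression, as usually understood, does not count death as an event, whereas PFS does. Under a literal reading of the Section 14 methods, a patient who dies without documented progression would be censored. Section 12 counts that patient as an event. The plan does not say which rule governs, nor what happens to a death after removal from study.

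Second, Kaplan-Meier estimation assumes that a censored patient has the same outlook as those still followed. A patient taken off for severe toxicity, or because the investigator judges it best, may well not. The plan has no sensitivity analysis for this and no report of why patients were censored.

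At stake is a named secondary endpoint in a single-arm trial of at most 24 patients, with no control arm in which a bias could cancel. Each removal is 1/24, about 4% of the sample. Some are foreseeable: Section 3 reports 3 dose-limiting toxicities among 22 patients in the earlier phase 1 study of this combination, and Section 11.0 warns that toxicities may be potentiated.

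**Working it through.** **Following one patient through the text.** A patient is removed for toxicity in week 12, after a week-8 scan showing stable disease.
- Footnote 6 waives the off-study CT, because the last scan is 4 weeks old. With 8-weekly scans, most departures fall under this waiver. So do early leavers whose baseline scan is under 8 weeks old.
- The 30-day visit is held. Stated follow-up then covers treatment-related adverse events only.
- With no event recorded, Section 14 censors the patient at the last on-study evaluation. A later progression is not looked for.
- A death within 30 days of the last dose would reach the trial through serious adverse event reporting (Section 17). A later death from cancer has no stated route.

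**The plan's own figures.** No planning value is given for PFS. The only design figure is the Simon design on response. Exact binomial calculation for 9 then 24 patients, stopping at 0 of 9 and requiring at least 3 of 24, gives type I error 0.0931 at 5% and power 0.9028 at 25%. This agrees with the stated 10% and 90%. Neither the rule nor the calculation uses PFS.

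**Size of a possible bias.** The inputs are assumptions, because the documents give none:
- on-study PFS exponential with median m = 4 months, so hazard λ = ln 2 / 4 = 0.1733 per month;
- a share q = 15% or 25% (3.6 or 6 of 24) removed before progression, so removal hazard c = λq/(1 − q) = 0.0306 or 0.0578;
- hazard after removal hλ.

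Kaplan-Meier censored at removal estimates exp(−λt), with median 4.0 months whatever h is. With full follow-up,

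S(t) = exp(−(λ+c)t) + [c / (λ + c − hλ)] × [exp(−hλt) − exp(−(λ+c)t)].

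Example, q = 25%, h = 3, t = 3.52: 0.4434 + (−0.2000) × (0.1604 − 0.4434) = 0.4434 + 0.0566 = 0.500. The true median is therefore 3.52 months.

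True medians against the censored 4.0 months:
- q = 15%: 4.14 (h = 0.5), 4.00 (h = 1), 3.82 (h = 2), 3.72 (h = 3)
- q = 25%: 4.27 (h = 0.5), 4.00 (h = 1), 3.69 (h = 2), 3.52 (h = 3)

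At h = 2 to 3, the overstatement runs from 4.0/3.82 = 1.05 to 4.0/3.52 = 1.14, that is 5% to 14%.

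**Extreme case.** If every removal counts as an event, the total hazard is λ + c = λ/(1 − q) and the median is m(1 − q): 4 × 0.85 = 3.4 or 4 × 0.75 = 3.0 months.

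**Other inputs.** Simulation with a 3-month median and 30% removed at h = 3 gives a true median of 2.57 against 3.0, about 17% (3.0/2.57 = 1.17).

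**The case against.** A reader might infer that the plan discards everything that happens after removal and that PFS is therefore overstated. The documents do not support either step.
- The censoring sentence applies only to patients without the event, and Section 12 places no limit on when a death counts. A known death after removal could be counted on a plain reading. The text leaves this open; it does not say such deaths are dropped.
- Footnote 6 is a safeguard, not the defect. When the off-study CT is done, it can show progression at departure.
- The direction of bias depends on an unknown. At equal hazard there is none, and at half the hazard the censored estimate is too low.
- Toxicity need not mean removal. Much of Section 11 interrupts, reduces or stops one drug, and for refractory hypertension it stops trametinib with follow-up continuing. Clinical decline is not a listed removal reason; it can only be inferred from investigator decision. No removal rate is given.

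The shift is also small against the precision available. Assuming 20 events and exponential PFS, an approximate 95% interval around 4 months is 4 × exp(±1.96/√20), or 2.6 to 6.2 months. PFS has no test or threshold attached.

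All of this limits the point. It does not remove the mismatch between the defined endpoint and the analysed one, or the absence of a rule for deaths after removal. Low precision is also no reason to leave a systematic error unexamined.

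One objection bears on the remedy. If later deaths are counted only when they happen to become known, follow-up depends on outcome and creates its own bias. Vital status must therefore be sought for every removed patient. Even then, a patient who progresses unseen and later dies is dated at death, which lengthens PFS.

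**Conclusion.** The point holds as a correction that should be made to the analysis of a secondary endpoint. Section 14 analyses time to progression where Sections 12 and 14 specify PFS. It censors removals without RECIST progression as non-informative and does not settle whether deaths, including those after removal, count.

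Overstatement of PFS is the likelier direction but is not demonstrated. It rests on removed patients having a worse outlook than those who stay. With an assumed 4-month median, 15-25% removed and 2-3 times the hazard after removal, the true median is about 3.5-3.8 months instead of 4.0. The Simon decision on response rate is unaffected.

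**What to change.** In Section 14:
1. Replace time to progression with PFS as defined in Section 12. Count any death without prior documented progression as an event, including a death after removal. State the vital-status follow-up this requires and apply it to all removed patients. OS needs the same information, and none is stated now.
2. Add one sensitivity Kaplan-Meier analysis that counts removal for toxicity or investigator decision, without RECIST progression, as an event on the removal date.
3. Report the number of patients censored, by reason.

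The cost is a few sentences, one further Kaplan-Meier run and vital-status contact after removal. The sensitivity estimate will look less favourable. No additional scans are required, but progressions after removal then stay unobserved, and the report should acknowledge this as a limitation.

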11.0 TOXICITIES/SIDE EFFECTS

Adverse events occurring in patients treated with trametinib and erlotinib may be 1) overlapping toxicities seen in both agents (i.e. rash, diarrhea, and pneumonitis); 2) toxicities typically associated with trametinib (i.e. visual disturbance, QTc prolongations) or 3) toxicities typically associated with erlotinib. However, toxicities with individual agents may be potentiated in the combination or unanticipated AEs may occur. The dose modifications may involve one or both agents, and should be based on the nature, severity, and attributions of the AEs. General guidelines are provided below. For safety and adverse event reporting, see **Section 17.0**.

While AEs may be thought to be related to individual agents for purposes of dose modifications, all toxicities will be considered related to combination therapy for description of AE profile.

11.1 Management of Erlotinib-Related Toxicities:

Toxicities with erlotinib that are likely (>20%) include:

- Fatigue
- Rash
- Diarrhea
- Decreased appetite
- Nausea/Vomiting

Toxicities with erlotinib that are less likely (<20%) include:

- Cough
- Shortness of breath
- Mucositis
- Abdominal Pain
- Changes in hair or nails
- Liver Toxicity

Side effects of erlotinib that are rare, but serious include:

- Pneumonitis
- Acute renal failure
- Stevens Johnson Syndrome
- Liver failure
- Conjunctivitis
- GI bleeding/perforation

The table below outlines the dose levels to be used for any necessary **erlotinib** dose modification:

If Dose level 0 of erlotinib (75mg daily) in the Phase 1 run-in is used for the phase 2 study:

Dose Reduction	Erlotinib Dose/Schedule
0	75mg QD
1	50mg QD
2	25mg QD

If dose level -1 of erlotinib (100mg daily) in the Phase 1 run-in is used for the phase 2 study:

Dose Reduction	Erlotinib Dose/Schedule
0	100mg QD
1	75mg QD
2	50mg QD

A maximum of two erlotinib dose level reductions are allowed. If a third dose level reduction is required, study treatment will be permanently discontinued.

Erlotinib Dose Modification for Toxicities Not Specified in Subsequent Sections

Erlotinib Treatment Modification for Clinically Significant Toxicities Deemed Related to Erlotinib (This section is not for specific AEs such as rash, pneumonitis, or diarrhea. Refer to other sections for these specific AEs).		
CTCAE v4 Grade	Dose Modification	Management Guideline
Grade 1	Continue erlotinib at current dose level.	Monitor as clinically indicated. Provide supportive care according to institutional standards
Grade 2	
 Consider interrupting treatment until resolution to grade 1 or baseline. Upon resolution, restart treatment at current dose level. 	
Grade 3	
 Interrupt treatment until resolution to grade ≤ 2 Upon resolution to grade ≤ 2, restart with one level of dose reduction 	
Grade 4	
 If the Grade 3 toxicity recurs, interrupt erlotinib; When toxicity resolves to grade ≤ 2, restart erlotinib reduced by another dose level 	
Erlotinib should be discontinued if treatment delay is ≥ 21 days due to toxicities. If the investigator concludes that continued erlotinib will benefit a patient, the study PI may be consulted for the possibility of resuming erlotinib provided that toxicities have resolved to grade ≤ 2 .		

11.2 Management of Trametinib-Related Toxicities:

Toxicities with trametinib that are likely (>20%) include:

- Fatigue
- Rash
- Diarrhea
- Nausea/Vomiting
- Leg or arm swelling
- Constipation
- Decreased appetite
- Decreased red blood cell count leading to fatigue

Toxicities with trametinib that are less likely (<20%) include:

- dehydration
- Cough
- Shortness of breath
- Itching
- Abdominal pain
- Dry skin
- Fever/chills
- Dizziness
- Pain in the bones
- Difficulty sleeping
- Dry mouth
- Headache
- Increases in blood pressure
- Loss of hair
- Headaches
- Blurry vision
- Changes or infection in fingernails

Side effects of trametinib that are rare, but serious include:

- Changes in the eye that can cause blindness or serious vision problems (Chorioretinopathy or central serous retinopathy (CSR), retinal vein occlusion (RVO), Retinal Detachment)
- Impaired heart function (decreased in cardiac ejection fraction)
- Liver failure or abnormalities in the liver function blood tests
- Pneumonitis
- Infections in the lung or urinary tract

Trametinib Dose Modifications

The tables below outlines the dose levels to be used for any necessary trametinib dose modification:

If Dose level 0 of trametinib (1.5mg daily) in the Phase 1 run-in is used for the phase 2 study:

Dose Reduction	Trametinib Dose/Schedule
0	1.5mg QD
1	1mg QD
2	0.5mg QD

If dose level -1 of trametinib (1 mg daily) in the Phase 1 run-in is used for the phase 2 study:

Dose Level	Trametinib Dose/Schedule
0	1mg QD
1	0.5mg QD
2	0.25mg QD

A maximum of two trametinib dose level reductions are allowed. If a third dose level reduction is required, treatment will be permanently discontinued.

Trametinib Dose Modification for Toxicities Not Specified in Subsequent Sections

Trametinib Treatment Modification for Clinically Significant Toxicities Deemed Related to Trametinib (This section is not for specific AEs such as rash, pneumonitis, diarrhea, liver chemistry, QTc prolongation, or visual changes. Refer to other sections for these specific AEs).		
CTCAE v4 Grade	Dose Modification	Management Guideline
Grade 1	Continue trametinib at current dose level.	Monitor as clinically indicated. Provide supportive care according to institutional standards
Grade 2	
 Consider interrupting treatment until resolution to grade 1 or baseline. Upon resolution, restart treatment at current dose level. 	
Grade 3	
 Interrupt trametinib if clinically indicated When toxicity resolves to Grade 1 or baseline, restart trametinib reduced by one dose level. If the Grade 3 toxicity recurs, interrupt trametinib; When toxicity resolves to grade ≤1, restart trametinib reduced by another dose level 	
Grade 4	
 Interrupt treatment until resolution to grade ≤1 Upon resolution to grade ≤1, restart with one level of dose reduction. If toxicity does not resolve to ≤1 or baseline, permanently discontinue trametinib. 	
Trametinib should be discontinued if treatment delay is ≥21 days due to toxicities. If the investigator concludes that continued trametinib will benefit a patient, the study PI and GSK medical monitor may be consulted for the possibility of resuming trametinib, provided that toxicities have resolved to grade ≤1.		

11.3 Specific Dose Modifications

11.3.1 Rash

Rash is a frequent AE observed in patients receiving trametinib and erlotinib (package insert). Recommendations for supportive care and guidelines for dose modifications for rash are based on experience with other MEK inhibitors and EGFR inhibitors.^{16,17} Patients should be informed that skin toxicity is expected during treatment with erlotinib and trametinib. Skin toxicity can take the form of dry skin, rash, acneiform eruption, and hair/nail changes. Prophylactic treatment of the skin with the recommendations below may prevent or reduce skin toxicity.

Patients with significant skin toxicity will be referred to dermatology for management. Recommended treatments may include topical therapy such as hydrocortisone cream or clindamycin gel. If needed, oral minocycline or oral doxycycline may be combined with topical therapy. For more severe cases, oral corticosteroids may be administered. Patients who fail to respond to these measures may have erlotinib and or trametinib interrupted, dose reduced, or discontinued.

Guidelines for Supportive Care of Rash	
Type of Care	Recommendations
Prevention/Prophylaxis^a	
 • Avoid unnecessary exposure to sunlight. • Apply broad-spectrum sunscreen (containing titanium dioxide or zinc oxide) with a skin protection factor (SPF) ≥ 15 at least twice daily. • Use thick, alcohol-free emollient cream (e.g., glycerine and cetomacrogol cream) on dry areas of the body at least twice daily. • Topical steroids and antibiotics should be applied at least twice daily, starting on Day 1 of study treatment, to affected body areas such as face, chest, and upper back. • Consider mild-strength topical steroid (hydrocortisone 1% cream) or topical antibiotic (e.g., clindamycin) or oral antibiotics (e.g., doxycycline 100 mg BID, minocycline 100 mg BID).
Symptomatic Care^b	
 • Pruritic lesions: Cool compresses and oral antihistamine therapies. • Fissuring lesions: Monsel's solution, silver nitrate, or zinc oxide cream. • Desquamation: Thick emollients and mild soap. • Paronychia: Antiseptic bath, local potent corticosteroids in addition to antibiotics; if no improvement, consult dermatologist or surgeon. • Infected lesions: Appropriate bacterial/fungal culture-driven systemic or topical antibiotics.

^a Rash prophylaxis is recommended for the first 6 weeks of study treatment.
 
^b Patients who develop rash/skin toxicities should be seen by a qualified dermatologist and should receive evaluation for symptomatic/supportive care management.
	

Trametinib/Erlotinib Dose Modification Guidelines and Management for Rash		
Rash Severity	Management Guideline	Dose Modification
Grade 1	
 • Initiate prophylactic and symptomatic treatment measures.¹ 	Continue trametinib and erlotinib at same dose level.

Trametinib/Erlotinib Dose Modification Guidelines and Management for Rash		
Rash Severity	Management Guideline	Dose Modification
Grade 2	Initiate prophylactic and symptomatic treatment measures. ¹	Continue at same dose level. If rash persists or worsens over 14 days consider dose reduction of trametinib and/or erlotinib by one dose level at discretion of investigator.
Grade 3		Suggest withholding erlotinib and/or trametinib until toxicity is grade ≤ 2 . If rash persists or worsens over 14 days, consider dose reduction at discretion of investigator. ²
Grade 4		Withhold trametinib and/or erlotinib until toxicity is grade ≤ 2 . Restart with trametinib and or erlotinib reduced by one dose level. ² If No recovery to \leq grade 2 within 4 weeks, permanently discontinue trametinib and/or erlotinib.
1. Rash prophylaxis is recommended for the first 6 weeks of study treatment. See above table. 2. Trametinib may be escalated to previous dose level if no rash is evident 4 weeks after restarting study treatment.		

